2. INTRODUCTION

2.1 STUDY RATIONALE

Alzheimer's disease (AD) is the major form of dementia worldwide. AD is a neurodegenerative disorder (NDD) with clinical trajectory unique to each patient and displaying several complex neuropathologies suspected to develop sequentially but which overlap at the time dementia is diagnosed²². These pathologies include extracellular amyloid beta deposits forming senile plaques, intracellular neurofibrillary tangles composed of hyperphosphorylated tau protein, synaptic degeneration, neuronal death, and central inflammation, which altogether produce an unalterable cognitive decline over time²³. Most therapeutic interventions targeting Alzheimer's disease until now have focused on monotherapies to alter a single neuropathology, including BACE1 inhibitors, gamma-secretase inhibitors and modulators, and active and passive immunization against amyloid beta. Unfortunately, very few of the therapeutic approaches tested to date have been able to significantly alter disease trajectory⁴⁴. This emphasizes the urgent need for novel therapeutic interventions to reduce several AD neuropathologies simultaneously. In fact, the complexity of AD likely requires combination therapies or pleiotropic agents⁴⁴. While the role of inflammation in AD remains enigmatic, it develops concomitantly with other neuropathologies¹³. Although previous attempts to lower neuroinflammation in humans have been inconclusive regarding disease trajectory and slowing of cognitive decline (including the now FDA-approved aducanumab and lecanemab), strategies targeting neuroinflammation in animal models are capable of mitigating AD-like pathologies.^{4,30}

Inflammation is pervasive to many neurological disorders, yet no clinical trial has demonstrated the efficacy of anti-inflammatory agents for AD. Interestingly, chronic peripheral low-grade inflammation is associated with aging and increases the risk for disease and mortality, including AD. Accumulating evidence indicates that nuclear factor-kappa B, tumor necrosis factor alpha (TNF α), interleukins (e.g. IL-1beta, IL-2, and IL-6), and chemokines (e.g. IL-8) are found elevated both in the blood and central nervous system (CNS) of AD patients. This suggests that proper and efficient modulation of neuroinflammation could be a viable intervention to alter disease trajectory in AD. In the present application, we intend to repurpose the FDA-approved drug Siponimod that is used to treat multiple sclerosis (MS) in early AD patients.

Throughout the protocol:

- The term 'study intervention' and 'study drug' refers to Siponimod and placebo in the double-blind treatment period.
- The term 'sponsor' refers to the entities listed in the Contact Information page(s)
- The term 'participant' refers to the common term 'subject'

2.2 BACKGROUND

Recently, the modulation of sphingolipids has been proposed as a possible avenue to treat AD, since they regulate synaptic plasticity, amyloidogenesis, and tau physiology⁶. A very potent signaling molecule involved in numerous cellular processes is sphingosine-1-phosphate (S1P). S1P is an extracellular phosphorylated form of the membrane lipid sphingosine present in the circulation and CSF that is bound to albumin and lipoproteins, such as ApoE⁶. S1P regulates cellular pathways by binding to five G-protein-coupled receptors, termed S1PR1-5, which are present in high levels in cardiac, vascular, immune, and brain cells⁵. Interestingly, S1PR are inhibited by organic compounds known as trifluoromethylbenzenes, which are derived from myriocin, a metabolite of the fungus *Isaria sinclairii*. Binding of the agonists/modulators to S1PR induces the internalization and intracellular sequestration of the receptors, thus inhibits the corresponding signaling pathways⁵. The pleiotropic actions of S1PR modulators have been a strong motivation for Novartis Pharmaceuticals to investigate them in the past 30 years to treat multiple sclerosis (MS). After successful testing in animal models and in clinical trials, the first S1PR modulator, fingolimod, obtained FDA approval for MS in 2010⁵. More recently, Novartis has developed a less cardiotoxic analog with higher specificity for SP1R1 and 5 named Siponimod, which was FDA-approved, also for MS, in 2019.

S1PR modulators are brain penetrant⁴, immunomodulatory, and neuroprotective in MS⁵.

Immuno-modulation is mostly achieved by preventing egression of lymphocytes from lymphoid organs, and the modulation of cytokine expression, including microglia⁵. For T lymphocytes, it was shown that S1PR modulators prevent the infiltration of CD8+ memory cells in the central nervous system (CNS). This property could be key for AD since, very recently, the group of Wyss-Coray showed that CD8+ T cells likely play a critical role in the adaptive immune response in the CNS of AD patients^{17,42}. On the other hand, the molecular mechanisms for neuroprotection are currently poorly understood. Nonetheless, both fingolimod and Siponimod lower the rate of brain atrophy in remitting relapsing MS (RRMS)⁷. Very interestingly, Siponimod was found to reduce brain atrophy at later stages of MS called secondary progressive MS (SPMS), making it the first drug with a demonstrated neuroprotective effect in SPMS¹². More precisely, at month 12 the percentage of total brain volume change from baseline adjusted mean were -0.28% and -0.46% ($p < 0.0001$) in Siponimod vs placebo-treated SPMS subjects, respectively²⁵.

Beyond MS, fingolimod was tested successfully in a 28-day clinical trial involving 30 amyotrophic lateral sclerosis (ALS) subjects taking the same dose as MS patients (0.5 mg/day)^{3\}, which constitutes precedence to repurpose S1PR modulators across NDD that have a strong inflammation component. The major adverse event (AE) findings in fingolimod vs. placebo-treated subjects were: 1 - A greater heart rate slowing (three participants had transient bradycardia but without clinical symptoms) in the hours after first dose, but not beyond 24h; 2 - Lower levels of circulating CD4+ and CD8+ T-lymphocytes, and CD19+ B-cells; 3 - A moderate increase in alkaline phosphatase levels in the first 4 weeks of treatment. Besides these AEs, which are similar to those reported in MS patients, there were no clinically significant abnormalities on routine blood counts, chemistries, urinalysis, and liver function tests³. Of note, two participants who were randomized despite being on QT-prolonging medications (sertraline and amitriptyline) completed the study without any severe AE³. Moreover, and very pertinent for AD, in 1 month-old 5XFAD mice (i.e. before plaque deposition onset, which starts at 2 months of age in this model) treated with 1 and 5 mg/kg/day of fingolimod for a period of two months were found to have significantly lowered A β 42 loads when measured by ELISA as well as lower levels of neuroinflammation when assessed by densitometric analysis of GFAP-positive astrocytes and Iba1 immuno-positive microglia in the hippocampus². Thus, the pleiotropic activities of S1PR modulators in AD mice and MS patients, combined with good safety and tolerability in other NDD, are hugely attractive in consideration of repurposing these agents for AD.

An important consideration when repurposing drugs is the degree of risk vs. potential benefit to patients. A major AE for fingolimod is the induction of transient bradycardia at dosing onset²⁹. This risk can be mitigated via a dose-escalation regimen²⁴ and by selecting subjects not prone to bradycardia. Because MS patients are younger than AD patients, we believe that cardiac risks are too high to test fingolimod in AD subjects. However, **Siponimod generates much fewer and less severe cardiac AEs** than fingolimod¹⁹, likely due to higher target selectivity for S1PR1 and 5⁵. It has been administered at **high doses** (10 mg/day for 18 days) in an up-titration regimen **without significant heart AEs**³⁸. This motivated us to repurpose Siponimod rather than fingolimod for AD. That said, Siponimod is ~80% metabolized by the hepatic cytochrome P450 enzyme, CYP2C9 and thus acts as a competitive inhibitor for these enzymes. Critically, the gene for CYP2C9 has several alleles. While individuals with *CYP2C9*1* are relatively safe, those with *CYP2C9*2* and **3* alleles experience higher inhibition of the enzyme by Siponimod (see section D.1.a. for more details)¹⁵. Altogether, AEs induced by S1PR modulators led MS experts and the FDA to recommend the following regimens for MS patients (drug label): 1 – Implementation of a daily escalation dose regimen for this class of drugs to manage the risk of heart block²⁷; and 2 – Set the maximum drug dose at 2 mg/day in *CYP2C9*1* subjects, but reduce the maximum dose to 1 mg/day for *CYP2C9*2* and **3* individuals¹⁵. In summary, the pleiotropic properties and manageable AEs of **Siponimod** make it a **very appealing candidate to repurpose** with the goal of altering both neuroinflammation and neurodegeneration, and thus the disease trajectory **of AD** if administered at an optimum regimen.

Our multidisciplinary group has pioneered the testing of immunomodulators for AD. First, we have evaluated the anti-cancer, a potent TNF- α modulator, thalidomide. Unfortunately, this drug proved too toxic for mild to moderate AD subjects, with many requesting to withdraw from the study early⁸. Currently, we are investigating lenalidomide in amnesic mild cognitive impairment subjects (NCT #04032626). For the present project, we have brainstormed with our multiple sclerosis (MS) specialty colleagues because MS is an NDD with a strong inflammatory component and with a pharmacopeia capable of reducing disease

severity³⁹. This inter-disciplinary teamwork resulted in a great interest to explore sphingosine-1-phosphate receptor (S1PR) modulators, particularly Siponimod, because they show both neuroprotective and immunomodulatory properties (see section C.). This collaboration led us to formulate the **central hypothesis that Siponimod could lower the rate of brain atrophy in AD subjects**.

To test our central hypothesis, we will carry out an 18-month Phase II, double-blind, randomized, two-armed, placebo controlled, proof-of-concept clinical study in early AD subjects (i.e. mild AD) who will be receiving an escalating dose of Siponimod or placebo in the ratio 2:1 for 12 months, followed by a 6-month washout period. The primary outcome measures are safety and tolerability of Siponimod in mild AD subjects. The secondary outcome measures are the rates of brain atrophy derived from volumetric MRI (vMRI) as a proxy for neurodegeneration conducted at baseline, 6, 12, and 18 months. The tertiary outcome measures are the changes in cognition and the levels of AD-associated (e.g., A β and tau) and inflammatory biomarkers in CSF after Siponimod exposure. In an exploratory effort, we will also measure plasma inflammatory markers during the entire duration of the study to investigate whether one or more of these markers can be used as dynamic surrogate markers of treatment response. Using our unique experience with the repurposing of immunomodulatory drugs for AD (and NCT #04032626), in the present project we are using elements of clinical trial design that we believe were successful and made some adjustments to fit the pharmacologic and toxic properties of Siponimod.⁸

3. RISK/BENEFIT ASSESSMENT

3.1.1 KNOWN POTENTIAL RISKS

Siponimod (formerly known as BAF312 and completed trial NCT #01665144) has been FDA approved since 2019 (IND #076122) for the treatment of multiple sclerosis. Most adverse events have been reported from MS patients, and very little is known about possible adverse events in subjects without MS. Most risks are associated with doses >2 mg/day. Most common adverse reactions (reported in >5%) are headache, hypertension, and transaminase increase (see Table 2).

Table 2: Summary of Adverse Events Reported in $\geq 5\%$ of Mayzent treated patients at a rate of at least 1% higher than in patients receiving placebo

Adverse reaction	MAYZENT 2 mg (N=1099) %	Placebo (N=546) %
Headache ^a	15	14
Hypertension ^b	13	9
Transaminase increased ^c	11	3
Falls	11	10
Peripheral edema ^d	8	4
Nausea	7	4
Dizziness	7	5
Diarrhea	6	4
Bradycardia ^e	6	3
Pain in extremity ^f	6	4

Terms were combined as follows:

- Headache, tension headache, sinus headache, cervicogenic headache, drug withdrawal headache, and procedural headache.
- Hypertension, blood pressure increased, blood pressure systolic increased, essential hypertension, blood pressure diastolic increased.
- Alanine aminotransferase increased, gamma-glutamyl transferase, increased hepatic enzyme increased, aspartate aminotransferase increase, blood alkaline phosphatase increase, liver function test increased, hepatic function abnormal, liver function test abnormal, transaminases increased.
- Peripheral edema, joint swelling, fluid retention, swelling face
- Bradycardia, sinus bradycardia, heart rate decreased
- Pain in extremity and limb discomfort

POTENTIAL SERIOUS ADVERSE EVENTS

+ *Bradycardia, Bradyarrhythmia, and Atrioventricular Conduction Delays*

Siponimod may cause the heart rate to slow, especially after taking the first dose. This issue will be mitigated by administering an EKG post dose at the 6-hour mark to assess for any potential adverse events. In addition, BP/HR will be checked hourly for 6 hours to assess for potential bradyarrhythmia or adverse events.

+ *Infections*

Siponimod lowers the number of lymphocytes, which may increase the risk of serious infections. Lymphocyte levels will be monitored by measuring a Complete Blood Count with differential at each in-clinic study visit.

+ *Liver Injury*

Elevations of transaminases may occur in Siponimod-treated patients. Caution should be exercised when using Siponimod in patients with a history of significant liver disease. We will mitigate potential for significant liver injury by routinely measuring levels via Comprehensive Metabolic Panel (CMP) which will be drawn at every in-clinic study visit.

+ *Increased Blood Pressure*

Siponimod-treated patients may experience an increase in systolic and diastolic pressure within 1 month of treatment initiation and persisting with continued treatment. During initial clinical trials of Siponimod it was noted that subjects experienced an increase in systolic pressure averaging 3 mmHg and diastolic pressure averaging 1.2 mmHg. Blood pressure will be monitored after each initial dose in titration schedule and at each subsequent visit. Blood pressure exceeding 160/95 after repeated testing will require investigator approval to continue in study.

+ *Macular Edema*

Siponimod may cause macular edema, which usually starts within the first 1 to 4 months after treatment onset. Macular edema may appear as early as 3 months following initiation of treatment with Siponimod, so subjects will be required to have baseline eye exam (within 12 months pre-dose initiation) and eye exam at scheduled intervals post-dose initiation per the study schedule of events. In clinical trials it was noted that macular edema occurred within the first four months of therapy.

3.1.2 KNOWN POTENTIAL BENEFITS

Potential benefits for subjects suffering mild AD dementia are unknown. However, Siponimod can reduce inflammation, mainly by sequestering CD8+ T memory cells in peripheral lymphoid organs, which limits their infiltration in brain tissues. Siponimod also modulates the expression of cytokines in several cell types, including in microglia⁵. Very recently, the group of Wyss-Coray showed that CD8+ T cells likely play a critical role in the adaptive immune response in the CNS of AD patients^{17,42}. In addition, although the molecular mechanisms are unclear, Siponimod was able to lower the rate of brain atrophy in remitting relapsing MS (RRMS)⁷. Very interestingly, Siponimod was found to reduce brain atrophy at later stages of MS called secondary progressive MS (SPMS), making it the first drug with a demonstrated neuroprotective effect in SPMS.¹² More precisely, at month 12 the percentage of total brain volume change from baseline adjusted mean were -0.28% and -0.46% (p<0.0001) in Siponimod vs placebo-treated SPMS subjects, respectively²⁵.

In summary, the potential benefits of Siponimod in mild AD dementia would be to reduce both neurodegeneration and inflammation, which are two major contributing mechanisms involved in the cognitive decline processes associated with dementia.

3.1.3 ASSESSMENT OF POTENTIAL RISKS AND BENEFITS

Given Siponimod has been FDA approved since 2019 (and its predecessor, fingolimod, was FDA approved in 2010), a significant amount of information is available from MS studies outlining the benefits and adverse events for this drug.

In this current clinical trial, our design incorporates specific strategies to enhance benefits while mitigating risks. We are selectively enrolling patients with mild AD dementia. Our approach involves initiating treatment at a conservative dose of 0.25 mg, gradually increasing to a final dose of 1.0 mg based on a predetermined titration schedule. Regular visits will include comprehensive safety assessments, encompassing procedures such as blood draws and EKGs, to diligently monitor for potential adverse events through the trial period.

+ Fetal Risk

Based on animal studies, Siponimod may cause fetal harm. For this reason, we will confirm that all female subjects are not pregnant at screening and are not of child-bearing potential (i.e. surgically sterile or LMP >12 months ago).

DRUG INTERACTIONS

In clinical trials it was noted that the following drug interactions can occur in participants. Due to this it was determined that the possible risks do not outweigh the benefits of potential treatment, and as such, the following drug classes will be deemed exclusionary.

+ Anti-Neoplastic, Immune-Modulating, or Immunosuppressive Therapies

- Siponimod has not been studied in combination with anti-neoplastic, immune-modulating, or immunosuppressive therapies. Caution should be used during concomitant administration because of the risk of additive immune effects during such therapy and in the weeks following administration.
- When switching from drugs with prolonged immune effects, the half-life and mode of action of these drugs must be considered to avoid unintended additive immunosuppressive effects.
- Because of the characteristics and duration of alemtuzumab immune suppressive effects, initiating treatment with Siponimod after alemtuzumab is not recommended.

+Anti-Arrhythmic Drugs, QT Prolonging Drugs, Drugs That May Decrease Heart Rate

- Siponimod has not been studied in patients taking QT prolonging drugs.
- Class Ia (e.g., quinidine, procainamide) and Class III (e.g., amiodarone, sotalol) anti-arrhythmic drugs have been associated with cases of Torsades de Pointes in patients with bradycardia.
- Because of the potential additive effects on heart rate, treatment with Siponimod should generally not be initiated in patients who are concurrently treated with QT prolonging drugs with known arrhythmogenic properties, heart rate lowering calcium channel blockers (e.g., verapamil, diltiazem), or other drugs that may decrease heart rate (e.g., ivabradine, digoxin).

+ Beta-Blockers

- Caution should be applied when Siponimod is initiated in patients receiving treatment with a beta-blocker because of the additive effects on lowering heart rate.

+ Vaccination

- During and for up to one month after discontinuation of treatment with Siponimod, vaccinations may be less effective.

- The use of live attenuated vaccines may carry the risk of infection and should therefore be avoided during Siponimod treatment and for up to 4 weeks after discontinuation of treatment with Siponimod.

+ CYP2C9 and CYP3A4 Inhibitors

- Because of a significant increase in exposure to Siponimod, concomitant use of Siponimod and drugs that cause moderate CYP2C9 and moderate or strong CYP3A4 inhibition is not recommended. This concomitant drug regimen can consist of a moderate CYP2C9/CYP3A4 dual inhibitor (e.g., fluconazole) or a moderate CYP2C9 inhibitor in combination with a separate - moderate or strong CYP3A4 inhibitor.
- Concomitant use of Siponimod and moderate (e.g., modafinil, efavirenz) or strong CYP3A4 inducers is not recommended for patients with CYP2C9*1/*3 and*2/*3 genotype.

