13. Each patient must be assessed for capacity to consent by the principal or sub-investigators in order to provide informed consent. If the patient is deemed unable to provide informed consent, they must have a legally authorized representative (LAR), and the LAR must review and sign the informed consent form. If the patient does not have a LAR, the patient must appear able to provide informed consent and must review and sign the informed consent form. If the patient is deemed unable to provide informed consent and does not have a LAR, they cannot participate in the study. In addition, the patient's study partner/informant (as defined in the study inclusion criteria) must sign the informed consent form. If the LAR and the patient's study partner/informant are the same individual, he/she should sign under both.
14. No active suicidality identified on Columbia-Suicide Severity Rating Scale (C-SSRS).
15. Patients with stable prostate cancer may be included at the discretion of the Medical Monitor.
16. Patients who are on monoclonal antibody medication for the treatment of Alzheimer's (ex. lecanemab, donanemab) for > 6 months or have discontinued monoclonal antibody medication for the treatment of Alzheimer's for > 6 months may be included if all other criteria have been met.

Exclusion Criteria

Subjects will be excluded if they have any of the conditions listed below:

1. Taking one of the following medications: Medications for treatment of cancer or other drugs that weaken the immune system (ex. Natalizumab and Rituximab), Amiodarone, Bishydroxycoumarin, Chloramphenicol, Cimetidine, Fluconazole, Fluvastatin, Miconazole, Phenylbutazone, Sulphinpyrazone, Sulphadiazine, Sulphamethizole, Sulfamethoxazole, Sulphaphenazole, Trimethoprim, and Zafirlukast.
2. Current active infection in participants including, but not limited to, herpes zoster, herpes infection, bronchitis, sinusitis, upper respiratory infection and fungal skin infection. Siponimod may increase the risk in participants with active infections.
3. If participant received mRNA COVID-19 vaccination, must have received last dose at least 3 months prior to first dose of study drug/placebo.
4. Current evidence or history within the last 3 years of a neurological or psychiatric illness that could contribute to

dementia, including (but not limited to) epilepsy, focal brain lesion, Parkinson's disease, seizure disorder, or head injury with loss of consciousness.

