7. STUDY POPULATION

INCLUSION CRITERIA

See table on page 5 for *inclusion*/exclusion criteria.

EXCLUSION CRITERIA

See table on page 6 for inclusion/*exclusion* criteria.

LIFESTYLE CONSIDERATIONS

Because of its ability to inhibit CYP enzymes, study subjects will be recommended to not eat grapefruit or drink grapefruit juice.

SCREEN FAILURES

Screen failures are defined as participants who consent to participate in the clinical trial but are not subsequently randomly assigned to the study intervention or entered in the study. The collection of a minimal set of screen failure information is required to ensure transparent reporting of participants who are deemed as a screen failure, to meet the Consolidated Standards of Reporting Trials

(CONSORT) publishing requirements and to respond to queries from regulatory authorities. Minimal information includes demographics and eligibility criteria.

Because of inherent daily variations in cognitive performance observed in the clinic, if MMSE score is outside of the range 20-26 at the initial screening, the PI may request MMSE retesting after a two week period.

Patients who do not meet one or more of the entry criteria will not be randomized and will be considered screen failures. Screen failures may be re-screened once per PI discretion for eligibility.

STRATEGIES FOR RECRUITMENT AND RETENTION

The clinical trial aims to recruit a total of 105 subjects from the study site, Barrow Neurological Institute (BNI). Study goal is to achieve a balanced enrollment, targeting approximately 50% male and 50% female participants. These study subjects will be outpatients diagnosed with mild AD dementia at BNI.

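### Section 3.1.3 declares cardiac drug classes exclusionary, but exclusion 1 names no cardiac class and lists only one of the eight cardiac drugs named in 3.1.3

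*Protocol*

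**What the plan says.** Protocol section 3.1.3, under Drug Interactions, states that "the possible risks do not outweigh the benefits of potential treatment, and as such, the following drug classes will be deemed exclusionary". Several headings follow. One is "Anti-Arrhythmic Drugs, QT Prolonging Drugs, Drugs That May Decrease Heart Rate". Beneath it the protocol warns of arrhythmia when the heart is already slow: "Class Ia (e.g., quinidine, procainamide) and Class III (e.g., amiodarone, sotalol) anti-arrhythmic drugs have been associated with cases of Torsades de Pointes". It goes on to advise, in general terms, against starting siponimod alongside arrhythmogenic QT-prolonging agents, and the same advice covers "heart rate lowering calcium channel blockers (e.g., verapamil, diltiazem), or other drugs that may decrease heart rate (e.g., ivabradine, digoxin"). Beta-blockers have their own heading, where the text is softer: "Caution should be applied when Siponimod is initiated in patients receiving treatment with a beta-blocker".

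For eligibility, section 7 refers to the synopsis: "See table on page 6 for inclusion/*exclusion* criteria". Exclusion 1 in that table opens with one class term, "Medications for treatment of cancer or other drugs that weaken the immune system", and then names individual drugs, beginning "Amiodarone, Bishydroxycoumarin, Chloramphenicol, Cimetidine, Fluconazole, Fluvastatin, Miconazole, Phenylbutazone" and ending with zafirlukast.

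Section 8, Prohibited Concomitant Therapy, bars treatment outside standard of care, gives a few non-cardiac examples, and adds whatever drugs the exclusion criteria list.

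**The concern.** One part of the protocol says that certain cardiac drugs keep a subject out. The list that screening staff are directed to use does not carry that rule. Two screeners reading different sections could reach opposite decisions on the same subject.

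Safety and tolerability are the primary objective. Section 3.1.1 puts bradycardia, bradyarrhythmia and conduction delay first among the potential serious adverse events, and its Table 2 shows bradycardia in 6% on siponimod 2 mg against 3% on placebo in MS patients. The Justification for Dose says there is no literature on siponimod's cardiac adverse events above age 60, while this trial enrols from 50 to under 85. Section 3.1.3 adds that siponimod has not been studied together with QT-prolonging drugs. The subjects whom 3.1.3 meant to keep out are those in whom added slowing of the heart or an arrhythmia would be most worrying.

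**Working it through.** No sample size, power or error rate is involved. The check is a drug-by-drug match, followed by a search for any other rule that closes the gap.

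**Step 1. Cardiac drugs named in 3.1.3, matched to exclusion 1**

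| Drug | Described in 3.1.3 as | In exclusion 1? |
|---|---|---|
| Quinidine | Class Ia anti-arrhythmic | No |
| Procainamide | Class Ia anti-arrhythmic | No |
| Amiodarone | Class III anti-arrhythmic | Yes |
| Sotalol | Class III anti-arrhythmic | No |
| Verapamil | Rate-lowering calcium channel blocker | No |
| Diltiazem | Rate-lowering calcium channel blocker | No |
| Ivabradine | Other rate-lowering drug | No |
| Digoxin | Other rate-lowering drug | No |

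Named: 4 + 4 = 8. Listed: 1. Missing: 8 − 1 = 7. Cardiac class terms in exclusion 1: 0. Beta-blockers appear in 3.1.3 only as a class, so they do not enter the count; exclusion 1 does not name them either.

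**Step 2. Could another rule catch the missing seven?**

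- Exclusions 8 to 10 concern conditions (hypertension, heart block, recent infarction or unstable coronary disease), not medications.
- Exclusion 22 is the investigator's case-by-case judgement.
- Prohibited Concomitant Therapy inherits the omission by referring back to the exclusion criteria, and its standard-of-care limb names no cardiac class.
- Elsewhere under Concomitant Therapy, only drugs that may affect cognition go to the medical monitor. For any other new drug the subject consults study staff, with no criterion given.
- The waiver footnote under the criteria covers departures from them. A drug that is not in the criteria never triggers that review.

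**Step 3. One subject, two sections**

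Take a subject on stable diltiazem who meets everything else. Under the declaration in 3.1.3 the subject is out. Under exclusion 1 the subject can be randomized unless the investigator objects. The same holds for sotalol.

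**Step 4. Is 3.1.3 consistent with itself?**

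The opening declaration is absolute. The cardiac bullet says that siponimod should generally not be started, and the beta-blocker bullet asks only for caution. The stated reason also points the wrong way: risks that fail to outweigh benefits would argue for admitting these subjects.

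**The case against.** **Section 3.1.3 is itself protocol text.** This is fair. Section 7 points to the table but does not say that the table alone governs. A reader might infer that the table overrides 3.1.3 and that these subjects are definitely eligible; the documents do not establish that. What stands is that the two places disagree and that screeners are directed to the one lacking the rule.

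**The over-broad text may be the declaration.** The cardiac bullet leaves room for judgement, so rewording 3.1.3 as caution would also remove the contradiction. That is a clinical decision for the sponsor. But the sponsor has already written that these classes are exclusionary, and carrying that through is the repair that follows its stated intent.

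**Other safeguards exist.** There is a screening EKG used for eligibility, a pre-dose baseline EKG, exclusions 9 and 10, a 0.25 mg start with biweekly steps to a 1 mg cap, and six hours of monitoring after the first dose at each strength. Section 2.2 also says that siponimod causes fewer and milder cardiac events than fingolimod. These points stand and lower the risk. None of them screens on the drugs in question by rule.

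**Tempting extensions that do not hold.**

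- A reader might infer that the vaccination heading contradicts inclusion 12 and exclusion 3. It does not: the vaccination bullets concern the period during and shortly after treatment, while those criteria concern vaccination before dosing.
- A reader might infer that leaving modafinil and efavirenz out of exclusion 1 is an error. Section 3.1.3 discourages them only in the CYP2C9 *1/*3 and *2/*3 genotypes, so their absence from a list for all subjects is not in itself wrong. The one inhibitor named under that heading, fluconazole, is listed.
- Nothing suggests bias between the arms. The mismatch acts before randomization.

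**Conclusion.** The contradiction is real and confined to the cardiac drugs. Section 3.1.3 declares the class exclusionary, while exclusion 1 has no cardiac class term and omits 7 of the 8 drugs named. Section 8 does not repair this. The conclusion rests only on the protocol's wording and needs no numerical assumption.

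Its practical size is unknown. The protocol gives no rate of use of these drugs in the target population, so neither the number of subjects affected nor any added risk of bradycardia can be estimated. It should be corrected because it is a safety-relevant entry rule that the sponsor has itself stated, and because the correction is cheap.

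**What to change.** 1. **Exclusion 1.** Add the classes already described in 3.1.3: Class Ia and Class III anti-arrhythmics; QT-prolonging drugs with known arrhythmogenic properties; heart-rate-lowering calcium channel blockers; and other rate-lowering drugs such as ivabradine and digoxin. State whether drugs such as sertraline and amitriptyline, which section 2.2 calls QT-prolonging, are in or out. State also that the stable cholinesterase inhibitor or memantine permitted in section 8 remains permitted. The protocol does not say that these two slow the heart; the clause only stops an open-ended class term from being read against section 8.
2. **Section 8, Prohibited Concomitant Therapy.** Name the same classes, so that none is started during dosing.
3. **Section 3.1.3.** Limit the exclusionary sentence to classes that are in exclusion 1, and put those worded as caution under a separate sentence. Give beta-blockers an explicit in or out, since a general term for rate-lowering drugs would otherwise take them in.
4. **Same sentence in 3.1.3.** Remove the negation, so that the risks are said to outweigh the benefits.

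The cost is a wording amendment. Concomitant medications are already reconciled at screening and at every scheduled visit, so no new procedure is needed. The downside is some additional screen failures, which the documents do not allow to be sized and which the existing medical monitor waiver can soften.
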